- If 72 hours after final dose escalation, there is no further improvement in SCr, continuation of terlipressin is at the discretion of the Principal Investigator at the clinical site.
- If a subject is initiated on RRT, terlipressin can be continued for a maximum of 72 hours after initiation of RRT.
- Terlipressin must be discontinued when the subject is to undergo liver transplantation, TIPS, or any other vasopressor therapy (single administration of vasopressor for cardiac stress test is acceptable)
- Dosing must be permanently discontinued if an event of cardiac ischemia or mesenteric ischemia occurs.

Retreatment:

If judged by the investigator to be potentially beneficial, subjects who demonstrate at least a partial response during the initial treatment course (at least 50% reduction in SCr) and develop recurrence of HRS-AKI may be retreated for a maximum of 14 days. To qualify for retreatment the subject must again meet the study inclusion/exclusion criteria. Retreatment may occur within 90 days of the subject's first dose of terlipressin.

Duration of Treatment:

For the Prospective Terlipressin Group, the active treatment period will be up to 14 days, allowing 1 retreatment cycle.

For both Prospective and Retrospective Subjects:

All subjects will be followed:

Post treatment clinical data collection will be through phone call and chart review. Creatinine, BUN and eGFR will be recorded per standard of care, recording mortality and the date of last dialysis (CVVH or HD) session for the following time points:

Collaborative Research Study, Version 4: 06/29/21
To Treat HRS-AKI Patients with Continuous Terlipressin Infusion

Day 7 +/- 2 days;
Day 14 +/- 3 days;
Day 30 +/- 1 week and
Day 90 +/- 1 week
Day 180 +/- 2 weeks and
Day 365 +/- 2 weeks.

For subjects who have a liver transplant Post Treatment

If the subject has a liver transplant recorded prior to the 90-Day visit (phone call or chart review), additional follow up will occur through one year after liver transplant.

Creatinine, BUN and eGFR will be recorded per standard of care, recording mortality and the date of last dialysis (CVVH or HD) session for the following time points:

Day 0 (date of transplant) – record allocation MELD and last calculated MELD prior to transplant;
Day 7 +/- 2 days;
Day 14 +/- 3 days;
Day 30 +/- 1 week,
Day 90 +/- 1 week,
Day 180 +/- 2 weeks and
Day 365 +/- 2 weeks.

Key Efficacy and Safety Data Assessment:

Primary Efficacy Assessment:

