5.1 Efficacy Variables

The efficacy variables are summarized below, and further details are provided in Section 13.

Primary Efficacy Assessment:

Improvement of renal function (SCr) from Day 1 through end of treatment, repeated measure analysis. SCr will be collected daily, from Day 1 through end of treatment. Baseline SCr will also be entered.

Secondary Efficacy Endpoints:

- Improvement of renal function (SCr) from Day 1 through end of treatment, repeated measure analysis as compared to the Retrospective Control Group.
- For the Prospective Terlipressin Group alone and also in comparison to the Retrospective Control Group:
 - Incidence of dialysis by Day 30 and Day 90 of follow up.

Collaborative Research Study, Version 4: 06/29/21
To Treat HRS-AKI Patients with Continuous Terlipressin Infusion

- Survival by Day 30 and Day 90 follow up.
- Transplant by Day 30 and Day 90 follow up.
- Serum creatinine at Day 30 and Day 90 follow up
- Serum creatinine and incidence of dialysis at Day 30, Day 90, Day 180, and Day 365 after liver transplantation and those alive without transplantation (transplant eligible and ineligible patients)
- Incidence of kidney transplant within one year after liver transplant.
- Descriptive analysis of number simultaneous liver kidney transplants and episodes of graft rejection at Day 90 and Day 365 after liver transplant.

Safety:

Safety review and assessments will be made only for the Prospective Terlipressin Group and will include the following:

- Serious adverse events up to 30 days after end of treatment.

6 Investigational Plan

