7.2 Number of Subjects to be Studied

Prospective Terlipressin Group - approximately 50 Terlipressin treated subjects. Retrospective Control Group - approximately 15-25 subjects per clinical site that were treated for HRS-AKI according to center's standard-of-care (Midodrine/Octreotide (M&O), albumin, or other vasopressor) that would have met the inclusion/exclusion criteria below as well as having critical clinical data points to enable a comparison of the Prospective and Retrospective groups. Retrospective cases collected from each site should include eligible patients starting from prior to site IRB approval for this protocol and going back to January 2015. Subjects enrolled in a blinded clinical trial in this time period are excluded.

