13.2 Secondary Efficacy Variables

- Improvement of renal function (SCr) from Day 1 through end of treatment, repeated measure analysis as compared to the Retrospective Control Group.
- For the Prospective Terlipressin Group alone and also in comparison to the Retrospective Control Group:
 - Incidence of dialysis by Day 30 and Day 90 of follow up.
 - Survival by Day 30 and Day 90 follow up.
 - Transplant by Day 30 and Day 90 follow up.
 - Serum creatinine at Day 30 and Day 90 follow up
 - Serum creatinine and incidence of dialysis at Day 30, Day 90, Day 180, and Day 365 after liver transplantation
 - Incidence of kidney transplant within one year after liver transplant
 - Descriptive analysis of number simultaneous liver kidney transplants and episodes of graft rejection at Day 90 and Day 365 after liver transplant

14 Serious Adverse Events

Only Serious Adverse Events will be collected for this study for the prospective group only. Safety review and assessments will be made only for the Prospective Terlipressin Group from time of first dose through 30 days after end of treatment. SAEs are collected from the start of study drug until 30 days after study drug was discontinued. Non-serious Adverse Events are not required to be collected for this study.

The investigator will record the nature, causality, severity, treatment, and outcome of the SAE, and will determine whether there is a “reasonable probability” that the study drug treatment caused the event.

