15.2 Secondary Analyses

A number of secondary outcomes will be examined for the study cohort. These outcomes include the incidence of dialysis, mortality, and liver transplantation at day 30 and 90. The

incidence of kidney transplant within one year of liver transplant will also be determined. Additionally, descriptive comparisons of SCr will be undertaken at day 30 and 90 of follow up and at 4 time points after receipt of liver transplantation (day 30, 90, 180 and 365) and also at similar time points for those patients who were transplant ineligible or did not undergo a transplant. Incidence will be calculated as the number of new events during the observation period divided by the total persons at risk. All statistical analyses will be conducted using Stata version 15.1 statistical software (StataCorp, College Park, TX). Statistical significance will be declared for a two-sided hypothesis test if the *P* value was <0.05.

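### The Day 30 and Day 90 SCr comparison takes whoever is alive with a chart value, so it mixes dialysed, transplanted and native-liver patients and can differ between groups without any renal effect

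*Combined protocol and SAP*

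**What the plan says.** Section 13.2 lists "Serum creatinine at Day 30 and Day 90 follow up" as a secondary variable. Section 5.1 sets the frame for it and its neighbours: "For the Prospective Terlipressin Group alone and also in comparison to the Retrospective Control Group". The only analysis text is in Section 15.2: "descriptive comparisons of SCr will be undertaken at day 30 and 90 of follow up".

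Four other places determine who contributes a value:

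- **Availability.** The Synopsis states "Creatinine, BUN and eGFR will be recorded per standard of care, recording mortality and the date of last dialysis (CVVH or HD) session". Follow-up is by phone call and chart review, so a creatinine exists only if care produced one.
- **Choice of controls.** Section 7.2 selects controls partly on "having critical clinical data points to enable a comparison of the Prospective and Retrospective groups".
- **Transplanted patients.** The Synopsis says "If the subject has a liver transplant recorded prior to the 90-Day visit (phone call or chart review), additional follow up will occur". The post-transplant visits are extra, and nothing withdraws these patients from the ordinary Day 30 and Day 90 visits.
- **Dialysis.** Table 1 schedules SCr at every follow-up visit and makes no exception for patients on RRT.

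The plan also contains partial safeguards. Section 15.2 reports the incidence of dialysis, mortality and liver transplantation at Day 30 and Day 90. It describes SCr after transplant at four time points, and "also at similar time points for those patients who were transplant ineligible or did not undergo a transplant". Section 5.1 words that last set as "after liver transplantation and those alive without transplantation (transplant eligible and ineligible patients".

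**The concern.** A creatinine at Day 30 or Day 90 means different things in different patients. With a native liver off RRT it reflects the kidney function that the drug is meant to improve. On dialysis it also reflects clearance by the machine. After a liver transplant it reflects removal of the cause of HRS, and after a simultaneous liver-kidney transplant it reflects a new kidney. The dead have no value.

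A summary over everyone with a value therefore depends on how many patients in each group have died, are dialysed or have been transplanted. There are reasons for those proportions to differ that have nothing to do with the drug's renal effect:

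- The groups are not randomised.
- Controls reach back to January 2015.
- Controls must have had at least 48 hours of treatment (Sections 6.1 and 8.4). No such minimum applies to terlipressin patients.
- Up to 25 subjects may be ineligible for transplant, which is as much as half of about 50 terlipressin subjects. No matching of controls on transplant eligibility is described.

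At stake is how one secondary result is read: a lower Day 90 creatinine in one group could be taken as lasting renal benefit when it reflects who survived or was transplanted.

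**Working it through.** **1. A yardstick from the plan.** The documents give no figure for Day 30/90 SCr. The nearest is the detectable difference for the primary endpoint in Section 15.3: 0.46 mg/dL at SD 1.00, with 50 versus 150 subjects, type 1 error 0.05 (two-sided per Section 15.2) and 80% power. Check: (1.960 + 0.842) × 1.00 × √(1/50 + 1/150) = 2.802 × 0.1633 = 0.458, or 0.460 with the t distribution. It reproduces, and is used below only for scale.

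**2. Deaths only, upper limit.** Assumed: the same underlying SCr distribution in both groups, SD 1.0 mg/dL, deaths of 30% and 40%, and every death from the top of the distribution. The mean of the lowest fraction p of a standard normal is −φ(z_p)/p.

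- 30% dead, p = 0.70: −0.3477/0.70 = −0.497
- 40% dead, p = 0.60: −0.3863/0.60 = −0.644
- Difference: 0.147 SD, so about 0.15 mg/dL lower in the group with more deaths

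**3. Deaths only, weaker link.** Same rates and SD, but with a logistic relation between SCr and death:

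| Log-odds of death per 1 mg/dL | Survivor mean, 40% minus 30% dead |
|---|---|
| 0 | 0.00 |
| 0.5 | −0.05 |
| 1.0 | −0.08 |

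**4. Adding transplant.** Section 3.5.2 describes a cohort of 62 transplanted patients, none with HRS reversal, of whom 76% were dialysis-free with SCr ≤1.5 mg/dL 30 days after transplant. Entry to this study requires SCr ≥1.5 mg/dL. Transplant can thus lower SCr without any drug effect.

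Assumed: native SCr mean 2.5 and SD 1.0, post-transplant SCr mean 1.2 and SD 0.4, and no true difference between groups A and B. If death is unrelated to SCr, the gap is (share of survivors transplanted in B − share in A) × (1.2 − 2.5). The last column is the range from simulation with log-odds of death of 0, 0.5 and 1.0 per mg/dL.

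| Rates, A versus B | Transplanted share of survivors | Formula | Simulated B − A |
|---|---|---|---|
| Deaths 20% vs 40%; transplants 20% in both | 0.250 vs 0.333 | −0.11 | −0.11 to −0.20 |
| Deaths 30% in both; transplants 20% vs 40% | 0.286 vs 0.571 | −0.37 | −0.30 to −0.37 |
| Deaths 20% vs 40%; transplants 20% vs 40% | 0.250 vs 0.667 | −0.54 | −0.52 to −0.54 |
| Deaths 30%, transplants 20% in both | 0.286 vs 0.286 | 0.00 | about 0.00 |

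Restricting to alive, untransplanted patients removes the transplant part. With deaths of 20% versus 40%, it still leaves between 0.00 (death unrelated to SCr) and −0.16 mg/dL.

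**5. Dialysis.** No figure is offered. The documents give no RRT rate and no basis for a typical SCr on dialysis.

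**6. Do the extra summaries repair the comparison?** Table 1 counts follow-up days from last dose, while Table 2 counts them from the transplant. The post-transplant Day 30 summary is therefore not the transplanted part of the Day 30 follow-up figure, and the two cannot be set against each other. The non-transplanted summary is closer to what is needed, but it is limited to survivors and includes values taken on dialysis.

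**The case against.** The strongest reply is that the plan already shows most of what a careful reader needs. Death, dialysis and transplant incidence at Day 30 and Day 90 will stand beside the SCr figures, for terlipressin alone and against controls. SCr is described separately after transplant and in the non-transplanted. The comparison is labelled descriptive, Section 15.3 concedes low power for the other secondary outcomes, and nothing claims that the Day 30/90 difference is a causal renal effect. The P<0.05 sentence in Section 15.2 is general and not tied to this item. The plan does not fix a mean or a median here, and restriction to patients alive with a value is inferred from silence.

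Most of this stands, and it is why the point is minor. Two things remain. Separate incidences do not show which patients supply the SCr values, and no summary sets dialysis values aside. The inference from silence is also sound: the dead have no creatinine, and neither imputation nor a composite is specified.

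A reader might go further and infer that the plan ignores death, dialysis and transplant, or that the group with more deaths or transplants will look better. The documents support neither. The events are reported, and the direction depends on event rates and on an SCr-death relation that the documents do not give.

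**Conclusion.** The point holds as a gap in linking and reporting. Followed as written, Section 15.2 yields a non-randomised Day 30/90 SCr comparison among survivors with a value, across three kinds of patient, and differing death, RRT or transplant rates can move it with no renal effect.

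Its size cannot be established from the documents. For 40% versus 30% deaths, 0.15 mg/dL is a ceiling, about a third of the 0.46 yardstick; milder assumptions give 0.00 to 0.08. The larger gaps of 0.30 to 0.54 mg/dL come mainly from assuming transplant rates of 40% versus 20%. With equal rates the distortion is about zero. All of these rest on assumed rates and SCr distributions and are illustrations, not predictions.

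It would be wrong to infer that the primary analysis is affected, since that concerns SCr from Day 1 to end of treatment, or that the plan favours terlipressin. Severity is low.

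**What to change.** In Section 15.2, replace the pooled Day 30/90 SCr comparison with a by-group table of mutually exclusive status at each time point, counted from last dose:

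- dead
- alive on RRT, whether or not transplanted
- transplanted and off RRT with an SCr value, with simultaneous liver-kidney recipients shown separately
- alive with native liver and off RRT with an SCr value
- alive and off RRT with no SCr value

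Summarise SCr only within the off-RRT classes, separately for transplanted and native-liver patients, and give the number contributing. State that these survivor-only summaries do not estimate a treatment effect.

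A ranked composite with death worst and RRT next may be added as an optional sensitivity analysis, but only if the plan says where transplanted patients and missing values are placed. Otherwise the mixing returns through the ranks. It also answers a different question from renal function.

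No new data are needed: the notes to Table 1 already call for survival, RRT and transplant status at every follow-up visit, and kidney transplants are recorded in Table 2. The cost is smaller numbers behind each SCr summary and a little more analysis work.

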^hVital sign measurements include body temperature, respiratory rate, systolic and diastolic blood pressure, SpO₂ (pulse oximetric saturation), and heart rate. Vitals will be taken at baseline (within 24 hours of start of study drug) and daily during study drug treatment days. The measurements should be assessed and recorded at a consistent, specific time of day. Preferable morning assessment/measurement.

ⁱConcomitant medications include IV solutions and blood products.

^jAll follow-up visits will include assessments of survival, RRT, TIPS and liver transplant status. Study days will be counted from the last day of study drug administration. If the subject is in the hospital during any of the Follow-up Time Periods, the study assessment data will be recorded from the subject's medical record.

^kAll study assessments are to follow SOC

^lOptional - Collection of Blood and Urine for future biomarker evaluation is optional and may be collected ± 1 day of target collection day

^mOptional - Cystatin C – assessment of cystatin c levels is optional – but if measured we want it assessed 3 times (at Baseline/pretreatment, on day 4 of treatment and last day of treatment)

ⁿCollection of last echocardiogram done prior to admission and any echocardiogram performed during admission, if performed as per standard of care

^oNeutrophils, lymphocytes, total protein, and magnesium if collected Standard of Care

^pEstimated Dry Body Weight is collected if calculated by site

Collaborative Research Study, Version 4: 06/29/21
To Treat HRS-AKI Patients with Continuous Terlipressin Infusion

Table 2 presents the schedule of assessments and procedures to be performed Post Transplantation.

Table 2 **Schedule of Assessments Post Transplantation**

Study Assessment ^c	Day of Liver Transplant	Follow-up Period (Days from Day of Liver Transplant)						
		7 ±2 days ^a	14 ±3 days ^a	30 ±7 days ^a	90 ±7 days ^a	180 ±14 days ^a	365 ±14 days ^a	Last Known follow-up date ^a
Record events of RRT, TIPS and mortality	X	X	X	X	X	X	X	X
Record all paracentesis events	X	X	X	X	X	X	X	X
SCr (BUN & eGFR if taken ^b)	X	X	X	X	X	X	X	X
MELD Score ^d	X							
Dialysis				X	X	X	X	X
Incidence of Kidney Transplant ^e	X	X	X	X	X	X	X	X

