15.3 Sample Size Considerations

A formal sample size calculation is not applicable for the proposed study. However, at least 50 subjects across more than 5-10 institutions may receive terlipressin treatment during the course of the intervention portion of the study. For the comparison of the terlipressin treatment group and retrospective controls, we expect to have 50 subjects in the intervention group and 150 subjects, assembled from the study sites, in the control group. Assuming a type 1 error of 0.05 and power of 80%, we expect to be able to detect a range of differences in serum creatinine (SCr) depending on the standard deviation of the change (primary endpoint) expected for the groups (see below). Based on results from the REVERSE trial, a change in SCr of as small as 0.05 mg/dL would be able to be detected if the standard deviation for the change approximated 0.10 mg/dL and a pre-specified sample size of 200 subjects, 50 of whom are in the intervention arm, is used for the calculation.

	Δ SCr mg/dL				
Detectable Difference	0.46	0.34	0.23	0.11	0.05
Standard Deviation	1.00	0.75	0.50	0.20	0.10

Given the relatively small number of subjects proposed for inclusion in this terlipressin study, we will likely be underpowered to detect a difference in the other secondary outcomes being explored.

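### Section 15.2 divides events by an undefined number at risk, so patients lost before Day 90, and for dialysis those who die first, can count as event-free

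*Combined protocol and SAP*

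**What the plan says.** Section 15.2 (Secondary Analyses) of the combined protocol and SAP names the outcomes: "These outcomes include the incidence of dialysis, mortality, and liver transplantation at day 30 and 90". It then gives a single formula for all of them: "Incidence will be calculated as the number of new events during the observation period divided by the total persons at risk". The phrase *at risk* is not defined. No section gives a censoring rule, a time-to-event method, a rule for competing events, or a rule for unknown status at Day 30 or Day 90.

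The rates are meant for comparison as well as description. Section 13.2 introduces them with "For the Prospective Terlipressin Group alone and also in comparison to the Retrospective Control Group", and 15.2 adds "Statistical significance will be declared for a two-sided hypothesis test", at the 0.05 level. Section 15.3 states the expected sizes: "we expect to have 50 subjects in the intervention group and 150 subjects, assembled from the study sites, in the control group". It also concedes that the secondary outcomes will probably be underpowered.

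On data collection, the Synopsis says "Post treatment clinical data collection will be through phone call and chart review". Footnote j to Table 1 (section 9.1) asks for survival, RRT, TIPS and liver transplant status at every follow-up visit, counted from the last dose. Section 7.4 allows withdrawal at any time. Control charts may go back to January 2015 (section 6.1).

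**The concern.** Two separate problems follow from the formula.

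*Loss.* If the denominator is everyone who entered the period, a patient whose record stops on Day 40 stays in it with no event. Mortality, dialysis and transplant are then all understated. If the extent of loss differs between a prospectively followed group and a group read from old charts, the comparison shifts for reasons unrelated to treatment. If lost patients are instead dropped from the denominator, the rate is a complete-case rate with a different bias. The plan does not say which applies.

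*Death before dialysis.* A patient who dies undialysed on Day 10 contributes a non-event to the dialysis rate. The introduction (section 3.1) calls the condition rapidly progressing and fatal, so such patients are to be expected. A lower dialysis rate could then reflect earlier death rather than better kidneys. Transplant before dialysis has no rule either.

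**Working it through.** The documents give no expected rate, sample size or power for dialysis, mortality or transplant, so there is no figure of the plan's own to reproduce. **All rates below are assumptions**, chosen to show direction and size. T is terlipressin and C is control.

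**1. Loss and mortality, plain reading.** Times to death and to loss are taken as exponential and independent over 90 days. With true mortality m and loss l, h = -ln(1-m)/90 and c = -ln(1-l)/90. The crude proportion is h/(h+c) × [1 - exp(-90(h+c))].

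For C with m = 0.45 and l = 0.30: 90h = 0.598 and 90c = 0.357, so h/(h+c) = 0.626. The second factor is 1 - 0.55 × 0.70 = 0.615. The product is 0.385.

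| True mortality, T vs C | Loss, T vs C | Crude mortality, T vs C |
|---|---|---|
| 40% vs 45% | 5% vs 5% | 39.1% vs 44.0% |
| 40% vs 45% | 10% vs 10% | 38.1% vs 42.9% |
| 40% vs 45% | 0% vs 10% | 40.0% vs 42.9% |
| 40% vs 45% | 0% vs 20% | 40.0% vs 40.8% |
| 40% vs 45% | 0% vs 30% | 40.0% vs 38.5% |
| 40% vs 50% | 0% vs 30% | 40.0% vs 42.9% |

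With no loss in T, the order changes once gradual control loss exceeds about 24% (40% vs 45%) or 41% (40% vs 50%). If all loss occurs at the start, the thresholds are 1 - 0.40/0.45 = 11% and 1 - 0.40/0.50 = 20%. The same 24% applies in the other direction if T is truly worse (45% vs 40%) and only T has loss.

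**2. Loss and mortality, other reading.** Take the same control group (m = 0.45, l = 0.30) but exclude lost patients. Observed deaths are 0.385. Those followed alive to Day 90 are 0.55 × 0.70 = 0.385. The rate is 0.385/(0.385 + 0.385) = 50%. The same data therefore give 38.5% or 50%, against a true 45%, depending on what *at risk* means.

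**3. Death before dialysis, no loss.** Let d and m be the Day 90 risks of dialysis and of death if the other could not occur, with hazards hd and hm derived as in step 1. The dialysis proportion is hd/(hd+hm) × [1 - (1-d)(1-m)]. Alive without ever having had RRT is (1-d)(1-m).

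| Group | d | m | Dialysis proportion | Alive without RRT |
|---|---|---|---|---|
| T | 30% | 30% | 25.5% | 0.70 × 0.70 = 49.0% |
| C, same dialysis hazard | 30% | 50% | 22.1% | 0.70 × 0.50 = 35.0% |
| C, higher dialysis hazard | 35% | 60% | 23.7% | 0.65 × 0.40 = 26.0% |

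In both control rows the group that does worse shows less dialysis. With d = 35% in C, this needs m above about 52%.

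**4. What a competing-risk estimator changes.** With complete follow-up, the step 3 proportion is exactly what the Aalen-Johansen estimator targets. It would return the same 25.5% and 23.7%. It handles censoring but does not restore the order. The last column of the table does.

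**5. Whether Kaplan-Meier is safe.** Only if loss is unrelated to prognosis. Suppose true mortality is 50%, a fraction L is lost at the start, and those lost have 25% mortality. The crude rate is 0.50 - 0.25L: 47.5% at L = 10% and 42.5% at L = 30%. Kaplan-Meier gives (0.50 - 0.25L)/(1 - L): 0.475/0.90 = 52.8% and 0.425/0.70 = 60.7%. Here its error (+2.8 to +10.7 points) is larger than the crude formula's (-2.5 to -7.5), so a sensitivity analysis is needed beside it.

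**The case against.** The strongest defence is that the plan intends complete status. Table 1 has RRT, TIPS, transplant and mortality monitored throughout follow-up, and a phone call supplements the chart. In the Synopsis the standard-of-care qualifier attaches to creatinine, BUN and eGFR rather than to mortality. With complete follow-up the crude proportion is a correct cumulative incidence. Mortality is also reported for the same groups at the same days, so a reader could see that a low dialysis rate came with high mortality. The Synopsis plans descriptive analysis, and the outcomes are secondary. All of this stands, and it limits the point. It supplies no rule for patients whose status is not obtained, and separate mortality figures do not show how many patients were alive and free of RRT.

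A reader might infer three stronger things that the documents do not support.

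- *That loss falls mainly on controls.* This is inference from the design. Section 7.2 requires controls to have critical data points, which may select for fuller records.
- *That the plan itself foresees loss in the main cohort.* The "Last Known follow-up date" column belongs to Table 2, the post-transplant schedule, and says nothing about Day 30 or Day 90 after treatment.
- *That the formula will favour the wrong group.* Reversal needs markedly unequal loss, or a large mortality difference with a small dialysis difference. The documents give no rates from which to judge either.

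**Conclusion.** The concern holds in this form: the denominator is undefined, unknown status has no rule, and the dialysis rate cannot be read as renal benefit without a companion measure. Under assumed rates, 30% gradual loss in one group alone turns a true 40% vs 45% into 40.0% vs 38.5%, while equal loss of 5-10% leaves a five-point gap at 4.8-4.9 points. The loss results rest on exponential times and non-informative loss.

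The two problems should be kept apart. Loss can affect all three outcomes. Death before dialysis affects the dialysis endpoint only and does not bias survival. Nor does it show that the dialysis arithmetic is wrong: the proportion is a valid cumulative incidence that answers a narrower question than the one of interest. Priority is moderate.

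**What to change.** Amend section 15.2 as follows.

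1. **Survival.** Use Kaplan-Meier estimates at Day 30 and Day 90, censored at last known contact, from a time origin stated for both groups. Table 1 counts from the last dose of study drug, which controls did not receive. Report the number lost by group, with a best/worst-case analysis that counts the lost first as all alive and then as all dead, because censoring may be informative.
2. **Dialysis and transplant.** Use cumulative incidence with death as a competing event, and also transplant as a competing event for dialysis. The purpose is to handle censoring.
3. **Companion measure.** Report and compare the proportion alive without RRT at Day 30 and Day 90 beside the dialysis rate. State whether this means never dialysed since the origin or off dialysis on the day.

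The cost is a little more analysis and one data check. Table 1 records RRT throughout, but the Synopsis names only the date of the last dialysis session. The CRF and the control chart extraction should therefore be confirmed to capture the date of first RRT, and changed if they do not.
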